Advancement to higher combination dose levels during the escalation phase will occur after an evaluation of safety and tolerability by the Dose Committee. The proposed continual reassessment method (CRM) will generate dose combination recommendations. The model estimates the probability of dose limiting toxicities (DLTs) in Cycle 1 (C1) at each candidate combination dose level to determine the dose combination to treat the next cohort. The MTD is selected as the combination associated with the highest posterior probability of DLT rating within the target interval of 25% - 35% and which have been used to treat at least 6 participants.

During escalation, a minimum of 3 participants on a combination dose level are required to be DLT evaluable to render a decision to proceed to the next dose level. A 4th participant, if available, may enroll onto the escalation dose before the first 3 participants have completed the DLT evaluation. DLT events for all participants at a given combination dose level will be entered into the CRM model and assessed by the Study Dose Committee. The first cycle (28 days) constitutes the DLT assessment period. Parallel Dose-Escalation Cohorts may be allowed.

***Dose-Expansion Component:*** After the Dose-Escalation Component has ended and the RP2D is determined, a Dose-Expansion cohort of up to 90 participants (including those already enrolled at this dose in the Dose-Escalation and Expansion cohorts) will be enrolled at the RP2D. In this Dose-Expansion cohort, up to 15 participants in each of the 6 genotypic/histotypic cohorts will be enrolled.

Moreover, once the Dose-Escalation Component has reached a threshold of activity based on clinically meaningful reduction in tumor burden at a dose with acceptable toxicity, additional participants may possibly be enrolled at dose levels prior to the determination of RP2D. The Dose Committee will determine whether clinically meaningful reduction has been achieved (eg,  $\geq 30\%$  reduction in the sum of longest diameters of target lesions or a lesser diminution with a preponderance of clinical evidence of benefit). See 'Dose-Escalation and Expansion Committee Charter' for more information.

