Expansion prior to RP2D may occur at more than one dose level. The current Dose-Expansion cohort will stop enrollment after the next higher dose combination in the Dose-Escalation Component is completed. At this point, the Dose-Expansion Cohort at the new higher level will open for enrollment if the dose is considered to have acceptable tolerability during the Dose-Escalation Component. Parallel Dose-Expansion cohorts may occur. A maximum of 12 participants (in both Dose-Escalation and Expansion cohorts) may enroll in each dose combination level. Once a dose level is expanded to include more slots, the sponsor may choose to reserve slots for genotypes/histotypes which are considered more likely to obtain clinical benefit based on the emerging clinical and/or biomarker data.

[Redacted text block]

[Redacted text block]

[Redacted text block]

[Redacted text block]

[figure not shown]

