Moving to a higher dose of both agents is not allowed. Moving to a higher dose of one agent and a lower dose of the other agent is allowed. Skipping a dose level as specified above is not allowed, but intermediate dose levels of RMC could be explored. Parallel dose cohorts may be allowed if the collective safety data are supportive ([Appendix 10](#)). The data in both Dose-Escalation and Dose-Expansion Components ([Section 4.1.1](#), [Section 4.1.2](#)) will be combined to fit the model and determine the recommended dose combination to treat the next cohort of patients.

The Dose Committee will be responsible for evaluating the safety data during the DLT period and provide decisions regarding the actual dose escalation level based on safety data, updated model dose recommendations, and other relevant available information. The RP2D will be determined by the Sponsor based on the totality of the information available at all dose levels, combining the Dose-Escalation and Dose-Expansion Components, and should not exceed the MTD. The Dose Committee will determine regarding opening the Dose-Expansion Component.

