### 6.6. Dose Modification

#### 6.6.1. Dose Modification Rules

A 28-day cycle will be maintained, and dose interruption will be noted in the 28-day cycle schedule.

In the Dose-Escalation cohorts, there will be no dose reductions or modifications during C1, 28-day DLT assessment period unless a DLT has occurred. After C1 and in the Dose-Expansion cohorts, if a dose reduction is recommended, then the combination dose level should be the previous lower dose level considered to be tolerable in prior participants receiving that dose. If the previous lower dose level comprised of two parallel cohorts (ie, two combination dose levels), the investigator and sponsor Medical Monitor may choose one of two lower combination dose level based on the participant’s medical and study drugs history.

- [REDACTED]
- [REDACTED]
- [REDACTED]
- [REDACTED]
- [REDACTED]

[REDACTED]

[REDACTED]

[REDACTED]

Two types of dose modifications are allowed, “dose interruption” and “dose level reduction.” The decision will be per investigator, according to the dose modification criteria and guidelines outlined in [Section 6.6](#). Any allowed dose modification and any deviation from the intended dose (missed doses or overdoses due to participant error) should be documented on the dose electronic Case Report Form (eCRF).

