### **6.6.2. Dose Modification Criteria for RMC-4630 and Cobimetinib**

In general, dose adjustments should be based on attribution to a particular drug, if known. Certain adverse events are known to be associated with administration of cobimetinib (cobimetinib IB) whereas others have been observed with the administration of RMC-4630 in clinical or preclinical studies (RMC-4630 IB). [REDACTED]

The following principles apply to Dose Escalation component of the study and should be employed for Grade 3 and certain Grade 4 AEs.

- If the AE is a known toxicity of cobimetinib only, cobimetinib should be interrupted and then dose reduced one level if recovery to  $\leq$ Grade 1 occurs within 28 days. RMC-4630 should be continued at the same dose. However, at the investigator’s discretion, RMC-4630 may be held if the AE does not improve with holding cobimetinib. If the AE does not resolve within 28 days from onset, permanently discontinue cobimetinib.
- If the AE is suspected to be due to RMC-4630, RMC-4630 should be interrupted and then dose reduced one level if recovery to  $\leq$ Grade 1 occurs within 28 days. Cobimetinib should be continued at the same dose. However, at the investigator’s discretion, cobimetinib may be held if the AE does not improve with holding RMC-4630. If the AE does not resolve within 28 days from onset, permanently discontinue RMC-4630.
- If the AE is known for both drugs, hold both drugs until recovery to  $\leq$ Grade 1. Restart at a reduced dose of the drug that was last escalated by one dose level if the recovery to Grade  $<1$  is within 28 days. The second drug may also be dose reduced by one level at the investigator’s discretion and after discussion with the sponsor Medical Monitor.
- If the AE is unknown for either drug, hold both drugs until recovery to  $\leq$ Grade 1. Restart at a reduced the dose of the drug that was last escalated by one dose level if the recovery to grade  $<1$  is within 28 days. The second drug may also be dose reduced by one level at the investigator’s discretion and after discussion with the sponsor Medical Monitor.

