**Table 9      Dose Modification Guidelines for RMC-4630 and Cobimetinib**

[REDACTED]	[REDACTED]
[REDACTED]	[REDACTED]
[REDACTED]	[REDACTED]
[REDACTED]	[REDACTED]
[REDACTED]	[REDACTED]

[REDACTED]	[REDACTED]
[REDACTED]	[REDACTED]
[REDACTED]	[REDACTED]
[REDACTED]	[REDACTED]

[REDACTED]	[REDACTED]
[REDACTED]	[REDACTED]
[REDACTED]	[REDACTED]
[REDACTED]	[REDACTED]

Dose modifications may also occur following the first cycle (DLT assessment period) during the Dose-Escalation Component or Dose-Expansion Component (where applicable) in the following specific instances:

- Any participant who experiences a Grade 3 AE that constitutes a DLT may be considered for dose reduction to last dose cohort upon recovery of the AE to Grade 1 or baseline if deemed medically appropriate by the investigator and Medical Monitor. These participants will be considered to have experienced a DLT at the original dose and, therefore, will not be permitted to remain at the same dose.
  - For participants in the Final Expansion Cohort – if an AE/SAE occurs within the first cycle and meets the DLT definition, participant may dose reduce RMC-4630 to 100 mg D1D2.
- Any participant who experiences a < Grade 3 AE that does not constitute a DLT but that recurs more than once ( $\geq$  Grade 2) after recovering from the initial onset of the AE may be considered for a dose reduction upon recovery of the AE to Grade 1 or baseline if deemed medically appropriate by the investigator and sponsor Medical Monitor. Discontinuation of the study medications after third occurrence of the AE that is Grade 2 (intolerable) or Grade 3.
- Re-challenge at the same or lower dose may be considered after resolution of treatment-related or treatment-unrelated AEs provided the AE did not meet DLT criteria. If the AE recurs, dose modification may be considered.
- Continuation of a single agent RMC-4630 may be allowed if there is presence of, or potential for, clinical benefit as assessed by the investigator and sponsor Medical Monitor. The dose and schedule of RMC-4630 may be cross-referenced to the on-going monotherapy study RMC-4630-01. The options are:

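### Does pooling expansion data into the CRM bias the MTD, given that the bar on Cycle 1 dose reductions is written only for escalation cohorts?

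*Combined protocol and SAP*

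**What the plan says.** In the cobimetinib arm, Section 4.1.1.3 fits one continual reassessment model (CRM) per dosing schedule. Data from both components "will be combined to fit the model and determine the recommended dose combination to treat the next cohort of patients". The MTD is chosen against a 25-35% DLT interval with a 30% target, and Section 4.1.2 sets it after escalation and the expansion below the RP2D are complete. The synopsis (Overall Design) adds that "DLT events for all participants at a given combination dose level will be entered into the CRM model", and that "A maximum of 12 participants (in both Dose-Escalation and Expansion cohorts) may enroll in each dose combination level".

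Section 6.6.1 says that in the escalation cohorts "there will be no dose reductions or modifications during C1, 28-day DLT assessment period unless a DLT has occurred". Its next sentence opens "After C1 and in the Dose-Expansion cohorts, if a dose reduction is recommended" and sends such a participant to the previous tolerable level.

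Section 6.6.2 gives the reduction routes. Its list for Grade 3 and certain Grade 4 events opens "The following principles apply to Dose Escalation component of the study and should be employed for Grade 3 and certain Grade 4 AEs". The text after Table 9 covers changes made after the first cycle in either component. For a participant reduced after a Grade 3 DLT it states: "These participants will be considered to have experienced a DLT at the original dose". A sub-bullet covers the final expansion cohort: RMC-4630 may be reduced when a first-cycle event meets the DLT definition.

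Sections 4.1.1.3 and 9.3 (Table 15) remove a participant from the DLT-evaluable set only when doses were missed for reasons other than toxicity. Section 4.1.1.2 makes a dose intensity of 50% or less, caused by study-drug toxicity, a DLT in itself.

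**The concern.** A CRM assumes that the DLT outcomes recorded at a level describe Cycle 1 at that level. If escalation participants must hold their dose until a DLT occurs, and expansion participants may be reduced earlier, the two groups were observed under different conditions. An expansion participant reduced for toxicity short of a DLT stays evaluable and is entered as a non-DLT. If the reduction prevented a DLT and the participant is modeled at the assigned level, the estimated full-dose DLT rate is too low. The error runs one way, toward a higher MTD, and the MTD is a primary objective.

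The wording invites this reading. Section 6.6.1 names expansion alongside the period after Cycle 1, as if the Cycle 1 bar did not reach it. No visible sentence says at which dose a reduced, DLT-free participant enters the model.

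**Working it through.** **1. How much of the data could be involved.** Section 9.2 builds its total as 42 (escalation) + 24 (expansion below the RP2D) + 78 (further participants at the RP2D) = 144, which matches the stated figure. The MTD is set before the 78 enroll, so expansion supplies 24 of 42 + 24 = 66 participants, or 36%. At a full level of 12 with 6 from escalation, it supplies 6 of 12. The pooled share is not trivial.

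**2. Whether the DLT criterion catches such a participant.** Assume cobimetinib on 21 daily doses, a step from 40 to 20 mg (40 mg taken as the level between 20 and 60 mg), 7 full doses, a hold of h days, then the lower dose. Dose intensity is (7×40 + (14−h)×20) / (21×40):

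- h = 0: 560/840 = 67%
- h = 3: 500/840 = 60%
- h = 6: 440/840 = 52%
- h = 7: 420/840 = 50%, which is a DLT under Section 4.1.1.2

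On a D1, D2 schedule with 8 doses, the same step after 2 doses gives (2×40 + 6×20) / (8×40) = 200/320 = 62.5%. A moderate reduction can therefore fall outside the DLT definition.

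**3. Whether the plan provides a route to it.** Taking the visible routes in Section 6.6.2 in turn:

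- The Grade 3 and 4 principles are written for the escalation component.
- The route for events below Grade 3 is introduced as following the first cycle, and it needs the event to recur more than once.
- The one Cycle 1 reduction provision for an expansion cohort concerns the final expansion and requires an event meeting the DLT definition. That is the same condition Section 6.6.1 sets for escalation.

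None gives criteria for a Cycle 1 reduction before a DLT in expansion below the RP2D. The concern rests on one phrase in Section 6.6.1 that carries no trigger of its own.

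**4. How such a participant would be coded.** Evaluability is visible: a shortfall due to toxicity stays in. The outcome is visible: no DLT. Only the dose label is open. The synopsis estimates DLT probability at each candidate combination level and enters events by level. Section 6.6.2 uses the original dose for those who had a DLT. A participant who spent part of a cycle at each of two levels belongs to no single candidate level, so the assigned level is the natural label. Nothing visible suggests modeling by dose received.

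**5. Size if it happened.** These are raw single-level rates, not output of the trial's model, because the prior is not visible.

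- One averted DLT of 12 is 8.3 points: 5/12 = 41.7% becomes 4/12 = 33.3%.
- Under an assumed uniform prior, the posterior probability of 25-35% moves from 0.20 to 0.29, and that of more than 35% from 0.72 to 0.50.
- With 6 escalation and 6 expansion participants, true rate p and share f of expansion DLTs averted, the pooled rate is [6p + 6p(1−f)]/12 = p(1 − f/2):

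| True rate p | f = 10% | f = 25% | f = 50% |
|---|---|---|---|
| 40% | 38% | 35% | 30% |
| 35% | 33% | 31% | 26% |

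At 35% every result stays inside the interval. Crossing into it from above needs a true rate near 40% at a level already cleared in escalation, and about a quarter of expansion DLTs averted.

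**6. Whether an escalation-only refit would help.** It would drop every expansion outcome, DLTs included, and leave as few as 3 participants at a level. Exact 95% intervals are 10% to 65% for 4/12 but 4% to 78% for 2/6. It would still hold participants with toxicity-related missed doses short of the DLT criterion: 3 of 8 RMC-4630 doses missed leaves 62.5%, and 9 of 21 cobimetinib doses missed leaves 57%. A gap between the two fits would not identify reductions as its cause.

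**The case for a change.** The strongest case for acting is that the ambiguity sits in unredacted wording which sites must apply. Section 6.6.1 mentions expansion separately from the period after Cycle 1, and Section 6.6.2 says only that "Dose modifications may also occur following the first cycle (DLT assessment period) during the Dose-Escalation Component or Dose-Expansion Component (where applicable"), which permits later changes without forbidding earlier ones. The possible bias has a known direction. With 12 participants and a 10-point interval, one event matters. A sentence would close the matter cheaply.

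Part of this stands. The visible text does not say whether the Cycle 1 rule reaches expansion below the RP2D, and step 2 shows that the DLT criterion would not catch every moderate reduction. The rest is weaker. The parts of Sections 4.1.1.3 and 6.6.1 and of Appendix 10 where an answer would sit are redacted, and Section 9.4 places the full escalation and expansion rules in a separate simulation report. Silence in what can be read is therefore not evidence of a missing rule.

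A single-level shift in posterior probability also does not show a different MTD, because selection compares combinations. The D1, D2 schedule of the RP2D stated in Section 6.1.1 would have its own model under Section 4.1.1.3, so the 21-day arithmetic does not carry straight into it.

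**Conclusion.** No change to the plan is needed. This is a gap in detail that the analysts can fill sensibly: a toxicity-related shortfall stays evaluable, the outcome is what was observed, and the dose is the one assigned. The scope of the Cycle 1 rule is a matter of clinical conduct on which no view is taken here. A question to the sponsor, or a look at the unredacted text and the simulation report, would answer it.

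For any harm, a participant must be reduced in Cycle 1 before a DLT by a route the visible text does not describe, the reduction must avert a DLT, and the level must be close enough to the 35% bound for that to count. If all three hold, the cost is 8.3 points of raw rate per event at a level of 12. With a true 35% and up to half of expansion DLTs averted, the pooled rate stays inside the interval. True rates, averted shares and the uniform prior are assumptions, and no effect on the selected MTD has been shown.

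There are backstops. The Dose Committee uses all available safety data (Section 8.3.6) and makes the final dosing decision, with the model as one input (Section 4.1.1.3). Escalation tests the next level directly (Section 4.1). The escalation-only refit would cost precision and could not diagnose the bias, so it brings no gain.

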#### **4.1.2. Dose-Expansion Component**

Once a combination dose level during the Dose-Escalation phase has reached a threshold level of activity based on clinically meaningful reduction in tumor burden at a dose with acceptable toxicity, additional participants may possibly be enrolled at dose levels prior to the determination of RP2D. The Dose Committee will determine whether clinically meaningful reduction has been achieved (eg,  $\geq 30\%$  reduction in the sum of longest diameters of target lesions or a lesser diminution with a preponderance of clinical evidence of benefit). The decision to open the Dose-Expansion Component will be made by the Dose Committee. See Dose-Escalation and Expansion Committee Charter for more information.

Multiple Dose-Expansion and Escalation Cohorts may occur in parallel. The current Dose Expansion Cohort will stop enrollment after the next higher dose combination in the Dose Escalation Component is completed. [REDACTED]

In the case of parallel Dose-Expansion cohorts below the RP2D, slot assignment to parallel cohorts will be in an alternating manner. Please refer to [Figure 1](#).

The MTD and RP2D will be determined after the Dose-Escalation and the Dose-Expansion (below the RP2D) Components are completed. [REDACTED]

#### 4.1.3. Intra-participant Dose-Escalation

Intra-participant dose escalation may be allowed to provide patients with an opportunity to receive a higher dose to potentially derive greater benefit from RMC-4630 and cobimetinib combination. Participants will be allowed to escalate to a higher dose once it has been cleared by the Dose Committee. For intraparticipant dose escalation to occur, the request must be approved by the sponsor Medical Monitor. Additionally, the following criteria must be met:

- Participants should be able to tolerate the dose level at which they are enrolled, demonstrated by minimal dose holds and no dose reductions ([Section 6.6.2](#)). Participants who have previously had a  $\geq$ Grade 3 adverse event during the study will not be eligible for dose escalation unless the adverse event was clearly unrelated to study drugs. Low grade, ongoing adverse events will be evaluated on case-by-case basis and may restrict participant's eligibility to escalate.
- Participants should complete at least 2 cycles of treatment at the dose level cohort in which they were first enrolled into the study. In rare cases, a participant may be allowed to dose-escalate without completing 2 cycles of the treatment upon discussion with the Medical Monitor. A dose cannot be escalated before the DLT window ends.
- If there are two higher combination dose levels which are cleared by the dose committee, then the participant will be allowed to escalate to the highest dose level which was cleared by the Dose Escalation and Expansion Committee. If two higher parallel cohorts are being evaluated, the investigator—after discussion with the Medical Monitor—will determine which combination dose level the participant may escalate to.

After intraparticipant dose escalation occurs, if a participant experiences an AE that meets the definition of a DLT at the dose level which has already been cleared, the participant should be managed according to the dose modification guidelines specified in [Section 6.6.2](#). For any Grade 4 toxicities, treatment with RMC-4630 and cobimetinib should be discontinued.

#### **4.1.4. Duration of Therapy**

Participants will be permitted to remain on-study therapy until disease progression per RECIST v1.1, unacceptable toxicity, or other criteria for withdrawal are met ([Section 7.1](#) and [Section 7.2](#)), or end of study ([Section 4.3](#)), whichever occurs first. Participants will return to the clinical site for an EOT visit within 30 days after last treatment dose. Alternatively, participants may withdraw from the study at any time with or without cause and will be encouraged for EOT evaluation.

After termination of treatment, participants will continue on study for long-term survival follow-up every 3 months ( $\pm 2$  weeks), unless they withdraw consent for further follow-up or end of study.

The anticipated duration of the study is approximately 3 years, including 2 years of enrollment and 1 year of follow-up visits.

#### **4.1.5. Scientific Rationale for Study Design**

The first phase constitutes a Dose-Escalation Component, which has been designed to minimize the number of participants exposed to potentially subtherapeutic doses.

After the dose level achieves a threshold for activity ([Section 4.1](#)), Dose-Expansion Cohorts may be initiated. In the Dose-Escalation Component, assessment of safety and tolerability will be the primary endpoints and will be directly measured by the incidence of DLTs, AEs, and serious adverse events (SAEs).

The Dose-Expansion Component below the RP2D provides a further assessment of safety and the tolerability, PK, and PD effects, as well as the preliminary activity of RMC-4630 and cobimetinib combination therapy at potentially active doses. The Dose-Expansion Component is designed such that multiple cohorts below the RP2D will be assessed and will provide additional information on the therapeutic index of RMC-4630 and cobimetinib, including any potential differential impact of dose based on genotype and histotype.

For the RMC-4630 and cobimetinib arm, there is a concurrent but staggered enrollment strategy between the Dose-Escalation and Dose-Expansion Components. The Dose-Expansion Component begins only once a threshold for activity has been demonstrated during the Dose-Escalation Component ([Section 4.1](#)). Once a cohort in the Dose-Escalation Component has completed the DLT window, a Dose-Expansion Cohort at that dose may open at the same time as the next highest dose cohort in Dose-Escalation Component.

